## 17.11 MISSING DATE INFORMATION FOR ADVERSE EVENTS

The following imputation rules only apply to cases in which the start date for AEs is incomplete (i.e., partly missing).

## Missing month and day

- If the year of the incomplete start date is the same as the year of the first dose of study treatment, the month and day of the first dose of study treatment will be assigned to the missing fields
- If the year of the incomplete start date is before the year of the first dose of study treatment, December 31 will be assigned to the missing fields
- If the year of the incomplete start date is after the year of the first dose of study treatment,
   January 1 will be assigned to the missing fields

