#### 10.2 ADVERSE EVENTS

Adverse events will be coded by system organ class and preferred term using the *Medical Dictionary for Regulatory Activities*, version 25.1 or newer.

An AE will be considered as a treatment-emergent adverse event (TEAE) if the AE began or worsened (increased in severity or became serious) on or after the date of the first dose of double-blind study treatment.

A TEAE for treatment cycle 1 is an adverse event with onset after the initiation of study treatment or became serious after the initiation of study treatment for cycle 1.

In each of the analysis periods (treatment cycle 1 in the double-blind period, open-label period, BOTOX cycle, or BOTOX overall), a specific TEAE will only count once per participant, associated with its worst severity during the time period of interest. Unless stated otherwise, the methods of analyses described in this section will be applied to each of the study period.

TEAEs will be summarized for each treatment group by treatment cycle 1 in the double-blind period, open-label period, by BOTOX cycle, and BOTOX exposure overall. Participants will be counted according to the treatment received at baseline (Placebo or BOTOX 72 U) for treatment cycle 1. For open-label period and Any BOTOX exposure tables, participants will be summarized according to the treatment received at cycle 1 baseline and treatment received during open-label (Placebo/BOTOX 72 U or BOTOX 72 U/BOTOX 72 U and Total). The only

exception is BOTOX cycle 3, where participants will be summarized by BOTOX 72 U/BOTOX 72 U.

Overall summary of AEs will be provided on a per-participant basis for categories of TEAEs, treatment-related TEAEs, deaths, serious adverse events (SAEs), AEs leading to discontinuation, and possible distant spread of toxin (PDSOT).

The number and percentage of participants reporting TEAEs in each treatment group will be tabulated by system organ class (SOC) and preferred term, and further categorized by severity and causal relationship to the study treatment separately. If more than 1 AE is coded to the same preferred term for the same participant, the participant will be counted only once for that preferred term using the greatest severity and strictest causality for the summarization by severity and causal relationship.

The incidence of TEAEs will be summarized by preferred term and treatment.

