#### 17.2 TREATMENT CYCLES

A treatment cycle is considered to start on the day of treatment with study medication and end on the day prior to the next study treatment or on the study exit day if there are no subsequent treatments.

[figure not shown]

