## Missing day only

- If the month and year of the incomplete start date are the same as the month and year of
  the first dose of study treatment, the day of the first dose of study treatment will be
  assigned to the missing day
- If either the year of the incomplete start date is before the year of the date of the first dose
  of study treatment or if both years are the same but the month of the incomplete start date
  is before the month of the date of the first dose of study treatment, the last day of the
  month will be assigned to the missing day
- If either the year of the incomplete start date is after the year of the date of the first dose
  of study treatment or if both years are the same but the month of the incomplete start date
  is after the month of the date of the first dose of study treatment, the first day of the
  month will be assigned to the missing day

If the stop date is complete and the imputed start date as above is after the stop date, the start date will be imputed by the stop date.

If the start date is completely missing and the stop date is complete, the following algorithm will be used to impute the start date:

 If the stop date is after the date of the first dose of study treatment, the date of the first dose of study treatment will be assigned to the missing start date  If the stop date is before the date of the first dose of study treatment, the stop date will be assigned to the missing start date

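### SAP 17.11 imputes partial AE start dates against the first dose only, so an event that began after open-label retreatment can be counted in cycle 1

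*SAP*

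**What the plan says.** SAP 17.11 has four rules that matter for events starting after the first dose:

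- Year only, same year as the first dose: "the month and day of the first dose of study treatment will be assigned to the missing fields".
- Year only, a later year: "January 1 will be assigned to the missing fields".
- Day missing, same year, where the start month "is after the month of the date of the first dose of study treatment, the first day of the" month is used. A later year is treated the same way.
- Start wholly missing: "If the stop date is after the date of the first dose of study treatment", the start becomes the first-dose date.

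There is one override. "If the stop date is complete and the imputed start date as above is after the stop date", the stop date replaces the imputed start.

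SAP 17.2 defines cycles that "start on the day of treatment with study medication and end on the day prior to the next study treatment", or at study exit if no further treatment follows. SAP 10.2 reports TEAEs separately for cycle 1, the open-label period, each BOTOX cycle and BOTOX exposure overall. For the first of these, "Participants will be counted according to the treatment received at baseline (Placebo or BOTOX 72 U) for treatment cycle 1". SAP 10.0 assigns safety data after Day 180 but before retreatment to the double-blind treatment. Under SAP 4.0 both arms may receive open-label BOTOX, with Treatment 2 possible from the Day 180 to the Day 420 visit.

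**The concern.** First-dose anchoring is a usual convention when the only question is whether an event is treatment-emergent. Here a start date has a second job: it decides which cycle, and so which column, the event belongs to. All four rules use the earliest treatment as the reference point, or the start of a month or year, and never look at a retreatment date. An event caused by open-label BOTOX in a placebo starter can therefore appear as a placebo event in the double-blind table and be absent from the BOTOX tables.

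AE incidence is an endpoint of the primary safety objective (SAP 5.1), and the placebo arm is small. Tables of possible distant spread of toxin (SAP 10.3) and AEs of special interest (SAP 10.4) are also by treatment group. If such events are few, one misplaced event would show.

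**Working it through.** The plan gives no figure to reproduce, so the check applies its rules as written.

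**Two illustrative cases (invented dates, Treatment 2 at Day 180).**

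| First dose | Treatment 2 | True onset | Day missing becomes | Year only becomes | Counted in |
|---|---|---|---|---|---|
| 10 Feb 2021 | 8 Aug 2021 | 13 Aug 2021 | 1 Aug 2021 | 10 Feb 2021 | cycle 1 |
| 10 Sep 2021 | 8 Mar 2022 | 13 Mar 2022 | 1 Mar 2022 | 1 Jan 2022 | cycle 1 |

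The override only replaces a start with an earlier stop date, so it cannot move either event forward past Treatment 2.

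**Not every partial date moves.** With Treatment 2 on 8 Aug 2021, a day-missing event in September 2021 is set to 1 September and stays open-label. A year-only event in 2022 is set to 1 January 2022 and also stays open-label.

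**Share of true cycle 2 events put in cycle 1.** Assumptions: Treatment 2 equally likely on any of 365 calendar days, no Treatment 3, and onset equally likely on each day of the stated range after Treatment 2. The result does not depend on which study day Treatment 2 falls.

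*Day missing.* The event is misplaced if Treatment 2 is not on the 1st and onset falls in the same month. A month of L days gives L(L − 1)/2 such pairs of treatment day and onset day: 465 for 31 days, 435 for 30 and 378 for 28. Over a year this is 7 × 465 + 4 × 435 + 378 = 5,373 pairs.

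- Onset days 0–29: 5,373 / (365 × 30) = 49.1%.
- Onset days 0–120: 5,373 / (365 × 121) = 12.2%.

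*Year only.* The event is misplaced if onset is in the same calendar year as Treatment 2, unless Treatment 2 was on 1 January.

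- Days 0–29: (10,950 − 435 − 30) / 10,950 = 95.8%.
- Days 0–120: (44,165 − 7,260 − 121) / 44,165 = 83.3%.

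*Start wholly missing, stop date present.* 100%, by the rule itself.

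**Early-clustered onset.** Protocol 2.3 says adverse reactions generally occur within days to weeks of injection. Suppose Treatment 2 falls uniformly on day d of a 30-day month, with an exponential onset lag of mean m. The day-missing share is then (1/30) × Σ over d = 2 to 30 of [1 − exp(−(30 − d)/m)]. This gives 85% for m = 3 days, 72% for m = 7 and 54% for m = 14.

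**Scale (planned arm sizes, SAP 15.0).** One moved participant adds 1/90 = 1.1 points to the placebo cycle 1 rate, or 1/270 = 0.4 points to the BOTOX cycle 1 rate, if not already counted there for the same event.

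**What a simple latest-dose rule would do.** Always using the latest dose compatible with the known date parts puts 0% of true cycle 2 events in cycle 1. It moves true cycle 1 events the other way. With Treatment 2 at Day 180, and cycle 1 onset days 0–178 giving 365 × 179 = 65,335 pairs:

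- Year only: 49,225 / 65,335 = 75% move to open-label (55% for onset days 0–29).
- Day missing: 5,373 / 65,335 = 8%.
- Wholly missing: all.

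**The case against.** Several objections have force.

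- **Direction.** A reader might infer that the rule systematically raises the placebo rate and lowers the BOTOX rate. The documents do not support that. The pattern applies to placebo starters, about 90 of 360. For the other 270, a moved event leaves a later BOTOX cycle, raises BOTOX cycle 1 and stays within BOTOX exposure overall.
- **Size.** The 54% to 85% range rests on a chosen lag distribution that the documents do not give. TEAEs also include background events such as nasopharyngitis and headache (Protocol 4.2), which need not cluster after injection. The uniform-onset figures of 49% and 12% belong beside it.
- **Exposure.** Visits are monthly, and AEs are collected both before and after treatment at treatment visits (footnote to SAP Table 1). Partial dates, above all year-only or wholly missing ones, should be uncommon. The AE tables are descriptive, and Protocol 9.4.2.1 provides participant listings.
- **An inferred link.** The SAP does not say in words that the imputed date assigns the cycle, and table specifications are in a separate document. The available text offers no other onset date for the purpose.

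These limit the size and direction of the effect. They do not remove it: nothing in 17.11 uses the collection visit to bound the date, and no cycle-specific rule appears.

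**Conclusion.** The point holds as a gap in allocating events to cycles. Read with 17.2 and 10.2, the 17.11 rules can put an AE that began after retreatment into cycle 1 and, for a placebo starter, into the Placebo column. Given a day-missing date on an event that began after Treatment 2, the misplaced share runs from 12% to 85% across the onset assumptions shown. It is 83% to 96% for year-only dates and 100% for wholly missing starts with a stop date. These shares apply only to partially dated events, whose number is not given and is probably small, so the absolute effect is unknown.

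Two stronger readings should be resisted. The net bias in the cycle 1 comparison has no fixed sign. Nor does the rule compromise TEAE status: anchoring to the first dose remains conservative for that question.

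**What to change.** Amend SAP 17.11 to compare a partial AE start date with every treatment date, in this order:

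1. Bound the possible onset by the known date parts, the AE stop date, and the visit at which the AE was first recorded, including whether that was before or after treatment at a treatment visit.
2. If only one cycle remains possible, apply the existing rules but keep the imputed date within that cycle.
3. If more than one cycle remains possible, assign the date of the latest compatible study treatment.
4. State that the imputed date determines the cycle, and report a sensitivity AE table under the current rule.

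The cost is a few lines of SAP text and programming. The downside is that some true cycle 1 events may move to open-label, including BOTOX starters' events leaving the blinded comparison, so step 3 cannot simply be called conservative. The first-recorded-visit bound limits this, and the sensitivity table shows what remains.

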## Missing month only

 If only the month is missing, the day will be treated as missing and both the month and the day will be replaced according to the above procedure

## Missing day only

- If the month and year of the incomplete start date are the same as the month and year of
  the first dose of study treatment, the day of the first dose of study treatment will be
  assigned to the missing day
- If either the year of the incomplete start date is before the year of the date of the first dose
  of study treatment or if both years are the same but the month of the incomplete start date
  is before the month of the date of the first dose of study treatment, the last day of the
  month will be assigned to the missing day
- If either the year of the incomplete start date is after the year of the date of the first dose
  of study treatment or if both years are the same but the month of the incomplete start date
  is after the month of the date of the first dose of study treatment, the first day of the
  month will be assigned to the missing day

If the stop date is complete and the imputed start date as above is after the stop date, the start date will be imputed by the stop date.

If the start date is completely missing and the stop date is complete, the following algorithm will be used to impute the start date:

 If the stop date is after the date of the first dose of study treatment, the date of the first dose of study treatment will be assigned to the missing start date  If the stop date is before the date of the first dose of study treatment, the stop date will be assigned to the missing start date

# 17.12 MISSING DATE INFORMATION FOR PRIOR OR CONCOMITANT MEDICATIONS

For prior or concomitant medications, including incomplete (i.e., partly missing) start dates and/or stop dates will not be imputed.

If start or stop dates for medications are only partially reported but can be classified as prior to Day 1, then the medications will be included as prior medications.

If start or stop dates for medications are only partially reported and cannot be definitively classified as having stopped prior to Day 1, then the medications will be included as concomitant medications.

# APPENDIX A POSSIBLE DISTANT SPREAD OF TOXIN
